## **Procedures**

OB smokers (n=60) will be randomized to either a combined self-regulation plus large changes (SR) intervention in advance of smoking cessation treatment condition (n=30) or to a healthy lifestyle education (LE) in advance of smoking cessation treatment attention-placebo control condition (n=30) for 16 weeks. The study will include up to 18 groups each run in succession with approximately 4-6 participants recruited for each group in order to have 3-5 participants beginning each group. Groups will be randomly assigned to one of the two treatment conditions using a random number generator after participants have completed all pretreatment assessments. Participants will learn their condition assignment at the first treatment session. Feasibility and acceptability will be monitored. Assessment of smoking/abstinence and weight will be obtained at baseline, on Quit Day, and 1, 2, & 3-months post-quit.

Recruitment procedures- Participants will be recruited through print and electronic advertising (e.g., newspaper, magazine, listserv, websites, online ads), advertisements on buses or at bus stops, and via community outreach (e.g., providing study information and pamphlets to local physicians).

Initial screening: Interested individuals will be given several options for contacting the study and for completing initial eligibility screening depending on advertising modality (e.g., call the study telephone number, email the study email address, provide their contact information in an electronic interest form). Individuals will be given the option of either completing initial screening using an online screener or being contacted by study staff for telephone screening.

Phone screening: Individuals who are screened over the telephone will be contacted by study staff. They will be provided with a brief description of the study, and will be asked if they are interested in participating. Verbal consent will be obtained prior to the potential participant's completion of the phone screen using a bulleted consent form that includes key information. Individuals who indicate that they would like a copy of the consent document will be provided a copy via email.

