Self-regulation plus large changes in behavior (SR). The active intervention is based on self-regulation theory and is similar to interventions tested previously and shown to be effective in reducing weight gain and weight regain. The initial 8-week program will include weekly group sessions focused on teaching self-regulation and efforts to produce a 10 lb weight loss to buffer against anticipated post-cessation weight gain based on the SR approach. The key concepts of the intervention: Self-Regulation. Participants will be taught the core self-regulation skills for controlling their weight: a) weighing themselves daily; b) detecting small changes in weight as soon as they occur; c) implementing problem-solving skills and learned strategies to combat changes in weight; d) evaluating the success of strategies implemented; e) rewarding themselves for successful weight loss and weight maintenance or f) making behavioral changes if weight gain occurs. These strategies are introduced over the course of the 8 weeks, with the initial weeks stressing the importance of daily self-weighing and learning to use the scale for information (rather than self-evaluation). At the end of the initial 8 weeks, the participants will be introduced to a color-coded system to help them accomplish steps b-f of the self-regulation model. The goal for the first 8 weeks of the program will be to lose 10 lbs in order to buffer against expected weight gain. To accomplish this, participants will be given a reduced calorie goal (1200-1500 kcal/day if <200 lbs or 1500-1800 kcal/day if >200 lbs). They will be instructed to self-monitor their intake and taught strategies for reducing caloric intake (e.g. reducing fat content of foods) and strategies for dealing with high-risk situations such as eating out. Structured physical activity, which is activity similar in intensity to brisk walking that lasts at least 10 minutes, will also be prescribed and self-monitored, starting with a goal of 50 minutes per week (10 minutes per day on 5 days per week) and gradually increasing to 150 minutes per week.

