Weeks 9-16 will focus on smoking cessation, but each session will include a private weigh-in and brief group discussion of strategies to maintain weight loss and prevent post-cessation weight gain. To maintain the weight losses achieved thus far and prevent post-cessation weight gain, participants will be taught to use a color zone system (Red, Yellow, Green) for weight maintenance to guide their behavior after completing the initial 8-week weight control program. The weight goals used to define the zones will be individually tailored based on the initial weight changes. Participants will be encouraged to weigh themselves daily and at the end of each week and to assess their current weight relative to their individual color zones. If participants are in Green, they will be encouraged to reinforce their success (with a sticker or small amount of money); if they are in Yellow they will be taught to begin monitoring their behavior more carefully and identify area to make changes to get back on track; if they are in Red, they will be encouraged to return to full self-monitoring of intake and activity and resume their original calorie intake and goals. During smoking cessation, the goal will be to minimize weight gain for those who achieved targeted weight loss as well as for those who did not. This Red, Yellow, Green system for weight maintenance has had demonstrable success in prior studies of the self-regulation model.

Healthy lifestyle education attention-placebo control (LE). Participants in this group will be provided with information on the obesity epidemic and the importance of a healthy lifestyle to use at their own pace as they wish. They will receive basic education about principles of healthy eating (e.g., simple vs. complex carbohydrates) and physical activity during the first 8 sessions. During sessions 9-16, the focus will be on smoking cessation. Sessions will also include lifestyle education information such as why weight gain occurs after smoking cessation. This group will not be taught any specific behavioral self-regulation skills to help them change their behaviors. Providing basic education about diet and exercise has produced minimal weight loss in other clinical trials.

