Patient adherence. Physical activity will be assessed using the Paffenbarger Activity Questionnaire (PAQ). Diet will be assessed using a questionnaire assessing frequency of eating behaviors (consuming sugar sweetened beverages, eating fast food) with measurable changes following the use of self-regulation strategies associated with weight outcomes. NRT use. Utilization of NRT will be assessed post-quit through weekly self-report using calendars. Utilization of a fitness app (SR condition only) will be recorded (e.g., number of days for which any dietary tracking occurred) during the weight management portion of the intervention (weeks 1-8).

Intervention outcome effects. Weight: Participants will be weighed in street clothes, without shoes. Weight will be measured at baseline, Quit Day, and post-quit follow-up sessions via an electronic scale. Timeline Follow-Back (TLFB): During each post-quit assessment, participants will be asked to report on smoking since the last assessment. Seven-day point prevalence abstinence will be based on self-report (7 consecutive days of no smoking) and biochemical verification. Exhaled Carbon Monoxide (CO): Alveolar CO will be assessed via the iCOquit® Smokerlyzer® CO  $\leq$  6 ppm, to verify self-reported abstinence on Quit Day and at post-quit follow-up sessions.

Process measures. These measures of theoretical processes will be collected at baseline and week 9 to explore effects of treatment on putative mechanisms and subsequent outcome variables. Self-efficacy. Smoking Self-Efficacy Questionnaire (SEQ-12): has two six-item subscales that measure confidence in ability to refrain from smoking when facing internal stimuli (e.g., feeling depressed) and external stimuli (e.g., being with smokers). Weight-efficacy after quitting smoking (WEAQ): is a six-item scale that assesses confidence to prevent weight gain after quitting smoking. Mood. The Positive and Negative Affective Schedule (PANAS): is a 20-item mood inventory with two scales that assess positive and negative affective states. Delay Discounting. Monetary Choice Questionnaire (MCQ): is a 27-item questionnaire that assesses preferences for either a smaller, immediate reward or a larger, delayed reward in order to calculate how quickly a reward diminishes in value as a function of its delayed receipt.

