#### Data Analysis Plan

Feasibility & Acceptability. Average monthly number of individuals screened and enrolled will show feasibility of screening and recruitment. The proportion of participants completing the final study assessment will show feasibility of retention. Response to SR & LE conditions. Attendance. The percentage of treatment sessions attended through week 10 (one week post-quit) will be calculated and compared between conditions; average attendance of  $\geq$  70% in both arms suggests good acceptability. Participant Feedback. Participant ratings of intervention satisfaction mean scores  $\geq$  3.5 (5-point scale) shows acceptability in each condition.

Intervention effects on treatment outcome variables: Based on ITT principles, all assigned participants will be used in analyses regardless of adherence and missing data. Participants with missing data will be assumed to have smoked and to have regained 0.3 kg/month (positive imputation) and analyses will be repeated using multiple imputation for sensitivity analyses. Generalized estimating equations (GEE) Group x Time analyses will be used for weight change and abstinence. Abstinence. The dependent variable of 7-day point-prevalence abstinence will be analyzed by time (Quit Day, 1, 2, 3-months post-quit) and conditions. Weight. The dependent variable of weight, will be analyzed by time (baseline, Quit Day, 1, 2, 3- months post-quit) and conditions. Secondary exploratory analyses will repeat the GEE analyses adding sex as a variable, and (separately) adding any/no weight loss at week 9 as a variable in predicting smoking abstinence.

Putative mechanisms will be examined using regression analyses to test the effects of treatment on proposed mechanistic variables at week 9, controlling for baseline values. Regression analyses will also test the effects of these proposed mechanisms on follow-up smoking outcomes. Notably, detection of statistically significant effects is not an objective in this limited-powered study.

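### The exploratory abstinence model uses week-9 weight loss only as any versus none, so it cannot estimate how abstinence varies with the amount lost; continuous change would be better

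*Combined protocol and SAP*

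**What the plan says.** The Data Analysis Plan analyses abstinence by GEE with condition, time and their interaction. It introduces one further model this way: "Secondary exploratory analyses will repeat the GEE analyses adding sex as a variable". The pre-quit weight term belongs to a second such model, described as "adding any/no weight loss at week 9 as a variable in predicting smoking abstinence". It sets no minimum loss, and that model uses neither the amount lost nor the programme's goal.

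The Procedures section gives the context:

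- **SR:** "The goal for the first 8 weeks of the program will be to lose 10 lbs in order to buffer against expected weight gain". For weeks 9-16 the stated aim is to "minimize weight gain for those who achieved targeted weight loss as well as for those who did not", so the protocol itself separates participants by whether they reached the target.
- **LE:** "Providing basic education about diet and exercise has produced minimal weight loss in other clinical trials".
- **Measurement:** "Weight will be measured at baseline, Quit Day, and post-quit follow-up sessions via an electronic scale", and "Participants will be weighed in street clothes, without shoes". Replicate weighing is not described and no measurement error is given.
- **Size:** "OB smokers (n=60) will be randomized", 30 per arm.

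**The concern.** Project Purpose argues that losing weight before quitting may protect against later gain, improve mood and raise self-efficacy, and so help people quit. The any-versus-none term is the only planned analysis that relates pre-quit weight loss itself to abstinence. Because it is cut at zero, it discards the amount lost.

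Specific Aims says the pilot is meant to yield preliminary effect sizes, and Project Purpose says it should inform a larger trial. A designer of that trial would want to know whether more loss goes with more abstinence. A yes/no contrast at zero does not answer that. It also becomes less informative as SR works better, because more SR participants fall on the same side of the cut. In LE, where little change is expected, the sign of a small measured change depends partly on weighing conditions.

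**Working it through.** The plan gives no figure to reproduce: no SD of weight change, no weighing error and no expected share losing weight. The means, SDs and errors below are assumptions, shown as ranges. The document inputs are the zero cut, the 10 lb goal (10 x 0.4536 = 4.54 kg) and 30 participants per arm.

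**1. Share counted as losing weight.** With measured loss normal with mean m and SD s, P(any loss) = Phi(m/s).

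- SR, m = 4.54 kg (mean equal to the goal): s = 3 gives Phi(1.51) = 0.935, about 28 of 30; s = 4 gives 0.872, about 26 of 30.
- SR, m = 2 kg: s = 3 gives 0.748, about 22 of 30; s = 4 gives 0.691, about 21 of 30.
- LE, m = 0 to 1 kg and s = 1.5 to 4 kg: 0.50 to 0.75, about 15 to 22 of 30.

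**2. Information kept by the zero cut.** If the effect is linear in kg, the information kept is the squared correlation of the flag with continuous change: phi(z)^2 / [p(1-p)], with z = m/s and p = Phi(z).

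The maximum is at z = 0: 0.3989^2 / 0.25 = 0.637, or 64%. For SR:

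| Mean loss (kg) | SD 3 kg | SD 4 kg |
|---|---|---|
| 2 | 0.54 | 0.58 |
| 3 | 0.44 | 0.52 |
| 4.54 | 0.265 | 0.39 |

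The SR range is therefore about 26-58%. Condition is in the model, so the pooled within-arm value also matters. Take SR mean 4.54 and SD 3, LE mean 0 and SD 2:

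- Average within-arm covariance of flag and change: (3 x 0.127 + 2 x 0.399)/2 = 0.59.
- Average within-arm variance of change: (9 + 4)/2 = 6.5.
- Average within-arm variance of the flag: (0.061 + 0.25)/2 = 0.155.
- Information kept: 0.59^2 / (6.5 x 0.155) = 0.34 to 0.35 (0.34 by simulation).

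**3. Wrong side of zero in LE.** Let one weighing have error SD e, so the difference of two weighings has error SD E = e x sqrt(2). With mean true change 0 and SD s, the share with the wrong sign is arccos[s / sqrt(s^2 + E^2)] / pi.

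- s = 3, e = 0.3 (E = 0.42): 4.5%. With a mean loss of 1 kg, simulation gives 4.2%.
- s = 2, e = 0.7 (E = 0.99): 14.6%.
- s = 1.5, e = 1.0 (E = 1.41): 24%.

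The range is about 4-24%.

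**4. Overlap with condition.** Use the same means and SDs as the pooled calculation.

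- Flag: the shares are 0.935 and 0.50, with average 0.717. The correlation with arm is [(0.935 - 0.50)/2] / sqrt(0.717 x 0.283) = 0.48, and the variance inflation is 1/(1 - 0.23) = 1.3.
- Continuous change: the between-arm variance is (4.54/2)^2 = 5.15 and the within-arm variance is 6.5. The correlation is sqrt(5.15/11.65) = 0.66, and the variance inflation is 11.65/6.5 = 1.8.

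**5. A cut at 10 lb instead.** P(loss of at least 10 lb) = 1 - Phi((4.54 - m)/s). In LE, with m = 0 to 1 kg and s = 1.5 to 4 kg, this is 0.001 to 0.188, or about 0 to 6 of 30. That is too sparse to be the model term.

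**The case against.** The analysis is labelled secondary and exploratory, and the plan says that finding significant effects is not an objective. The Group x Time analyses of weight and abstinence do not use the flag. The 10 lb goal is presented as a buffer against weight gain; nothing ties that amount directly to abstinence. Whether any pre-quit loss goes with abstinence is a coherent question, particularly if self-efficacy is the route. The raw weights are collected, so a continuous analysis remains possible later. All of this stands and keeps the point small. It does not make the zero cut the better form for the only model of its kind, and choosing the form afterwards would lose the benefit of prespecification.

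A reader might infer more than the documents support:

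- **That the flag largely restates condition.** Even with SR's mean loss set at the goal, its correlation with arm is about 0.48, and continuous change is more strongly tied to arm (0.66).
- **That zero lies within weighing error in LE, so the flag is noise there.** No error is stated. Under the errors tried, about 76-96% of LE participants are still classified correctly.
- **That the flag is almost constant in SR.** This treats the goal as the expected mean, while the protocol plans for participants who miss it. At a mean loss of 2 kg with SD 3 to 4 kg, about 8 to 9 of 30 would show no loss.
- **That a null result would count against the buffer idea.** The plan's own statement on significance argues against reading it that way.

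**Conclusion.** The point holds as a minor improvement. It is plain from the text that the term is binary, cut at zero and blind to the amount lost, so this model cannot estimate how abstinence varies with loss. The information figures (at most 64%; 26-58% in SR) require normally distributed change, an effect roughly linear in kg, and the assumed means and SDs. The 4-24% misclassification in LE depends on assumed weighing errors and true SDs. The direction is the same throughout these ranges; the exact size cannot be fixed from the documents. The documents do not support any claim that the main analyses are compromised.

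**What to change.** In the Data Analysis Plan, replace the any-versus-none term with weight change from baseline to week 9 as a continuous variable (kg or percent of baseline). Enter it in the Group x Time abstinence GEE already planned; condition is in that model, so nothing further is needed there. Any loss, and attainment of the programme's 10 lb goal, can be shown descriptively by arm, noting that few LE participants are likely to reach 10 lb.

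The cost is one line of wording, settled before analysis, with no new data: baseline and Quit Day weights are already collected. In return, the coefficient is read per kg (or per percent), assumes approximate linearity, and is somewhat more correlated with condition than the flag (variance inflation about 1.8 against 1.3 in the scenario above).

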### **Confidentiality**

Many precautions will be taken to minimize the risk of loss of privacy or confidentiality. The study consent form will inform participants of confidentiality guidelines and standards. Strict confidentiality will be maintained and records will be kept confidential to the level allowed by law. All staff will be trained in procedures for maintaining confidentiality of participant information. Only the investigative team and research staff will have access to non-anonymous records. Personal identifier records will be kept in a locked cabinet or on a secure Brown University computer server, and any forms with identifying information will be stored separately from other study data. Data collection forms will be identified by a unique identification number without personal identifiers. The identifier key will be stored separately from the data collection forms and accessible by the investigative team. Information provided by study participants will not be released to outside sources unless legally required or written consent is provided by the study participant.

## **D. POSSIBLE RISKS TO PARTICIPANTS, PLAN TO MINIMIZE RISKS, ANTICIPATED BENEFITS OF PARTICIPATION**

### **Potential Risks**

Potential risks are minimal and include:

1. Nicotine withdrawal or discomfort following smoking cessation (likelihood high; seriousness low): Upon quitting smoking some individuals experience increases in cravings to smoke, irritability, anxiety, depression, or appetite, changes in sleep, difficulty concentrating, feelings of impatience or restlessness, coughing, dizziness, nausea, or sore throat.
2. Adverse side effects from NRT (likelihood low; seriousness variable): In some individuals, the use of nicotine patch is associated with local skin reactions, mild difficulty sleeping, mild anxiety, (rarely) vivid dreams or nightmares. Local skin reaction in up to 50% of patients, usually mild and self-limiting; rotating patch sites is recommended or discontinuing patch treatment (fewer than 5% of patients). Difficulty sleeping is mild; patients can remove the patch before bedtime and replace it in the morning. The same is true for vivid dreams. Mild anxiety similar to the effects of smoking a few cigarettes is sometimes reported; dosage can be lowered. Common side effects of nicotine lozenges include mouth or throat soreness, indigestion, heartburn, sour or upset stomach, or nausea. These are generally mild and transient. While NRT is intended for use in place of smoking as a smoking cessation aid, some participants may smoke in reduced amounts while using NRT. Research on the effects of using NRT concurrently with cigarette smoking have found no evidence of dangerous consequences of such a practice, including use of up to 42mg of NRT for 2 weeks prior to cessation while continuing to smoke ad libitum. If participants were to smoke while using NRT, they may experience nausea as a side effect.
3. Excessive weight loss or development disordered eating (likelihood low; seriousness moderate to high): A potential risk of participation in a weight loss intervention is losing more weight than would be medically advisable including greater than 20% weight loss from baseline or reaching a BMI  $\leq 18.5$  (underweight). In a previous weight gain prevention study of 599 participants, 1.2% had greater than 20% weight loss from baseline and 0% reached a BMI  $\leq 18.5$ . Development of symptoms of disordered eating such as binge eating, excessive food restriction, or compensatory behaviors (e.g., purging, abuse of diet pills or laxatives) as a result of participation in a weight loss intervention is very rare. Previous research has shown that participation in weight loss treatment may actually decrease symptoms of disordered eating such as binge eating and disinhibited eating and does not affect dietary restraint. Similarly, participation in a self-regulation weight loss intervention that utilized daily self-weighing was not

associated with any adverse changes in psychological symptoms including disordered eating behavior. In a previous weight gain prevention study of 599 participants, 0% reported behavior triggering an eating disorder alert.

4. Breach of confidentiality (likelihood low; seriousness variable): One of the potential risks to participants is breach of confidentiality. It is possible that data collection could result in breach of confidentiality.

5. Emotional discomfort from answering questions about physical and emotional health.

### **Protection Against Risks**

Recruitment and Informed Consent. All study procedures will be consistent with the Helsinki Declaration in the protection of Human Subjects. We have made every attempt to minimize risks to participants throughout the study protocol, including loss of privacy or confidentiality, and any potential discomforts. We believe that our planned procedures (described below) will be highly effective for minimizing risk. During initial telephone contact, the nature of the project, the time and risks involved in this study, and inclusion/exclusion criteria will be described. If the potential participant continues to express interest, informed written consent will be obtained. A copy of the consent form will be provided to enrolled participants. The screening protocol will exclude individuals who would be at greater risk as a result of participation in the proposed research. Safeguards to protect against risks will be implemented and maintained throughout each phase of the research study.

